11.3	Medical Monitor Responsibilities.....	23

12	General Clinical Management.....	24
12.1	Data Recording.....	24
12.2	Clinical Monitoring.....	24
12.3	Study Product Accounting.....	24
12.4	Participant Compliance Monitoring.....	25
12.5	Unmasking of Study Information.....	25
12.6	Participant Payments.....	25
13	Administration Management.....	25
13.1	Relevant Standards.....	25
13.2	Deviations from the Protocol.....	25
13.2.1	Major Protocol Deviations.....	25
13.2.2	Minor Protocol Deviations.....	26
13.3	Modifications to the Clinical Investigational Plan.....	26
13.4	Termination of the Study.....	26
13.5	Data Protection.....	26
13.6	Data Handling and Record Keeping.....	27
13.7	Reporting.....	27
13.8	Study Registration.....	27
13.9	Publication Policy.....	27
		
13.11	Indemnity.....	27
14	References.....	28
15	List of Abbreviations.....	28
16	Appendices.....	29
16.1	Appendix A:.....	29
16.2	Appendix B:.....	30

1 Overall Synopsis

Study Sponsor	Allergan Pharmaceuticals International Ltd. [name].
Title of Study	Optive Brand For Day And Night Dry Eye Management
Protocol Number	CMO-EAME-EYE-0485
Phase or type of study	The study will be an open label, bilateral, prospective, interventional post marketing, clinical study.
Investigator(s) / Site(s)	OCULAR TECHNOLOGY GROUP - International (OTG-i), [name].
Planned Duration of Study	6 months
Study Population	Up to 40 participants to have 35 participants enrolled into the investigational phase at the end of Visit 2 to achieve a cohort of 30 participants completing the study.
Inclusion Criteria	The inclusion criteria will include the following: 
 • Age at least 18 years; • OSDI score of ≥ 23; • Ocular comfort at waking <65 on 100-point scale; • Conjunctival staining Grade ≥ 2 (scale 0 to 4) in at least one eye; • Use of eyedrops for the relief of dry eye symptoms for at least one month.
Exclusion Criteria	The exclusion criteria will include the following: 
 • Use of Benzalkonium Chloride (BAK) preserved eyedrops in the last month; • Use of Optive brand eyedrops in the last month; • Contact lens wear during the study; • Known pregnancy or lactation during the study period; • Enrolment of investigator's office staff, relatives, or members of their respective households; • Participation in any clinical trial within 30 days of the enrolment visit.
Planned Start Date	July 2017


Objective(s)
	
The primary objectives of the study will be to:
 
 i. Quantify the effect of a one-month treatment involving an eyedrop / gel combination on overall dry eye symptomatology on moderate to severe dry eye sufferers; ii. Evaluate the effect of a one-month treatment involving an eyedrop / gel combination on conjunctival staining moderate to severe dry eye sufferers. 
The secondary objective of the study will be to quantify the effect of a one-month treatment involving an eyedrop / gel combination on symptomatology upon waking on moderate to severe dry eye sufferers.

Hypotheses
	
The primary hypotheses that will be tested will be that:
 
 i. One-month treatment of moderate to severe dry eye sufferers with an eyedrop / gel combination will reduce overall dry eye symptomatology; ii. One-month treatment of moderate to severe dry eye sufferers with an eyedrop / gel combination will decrease conjunctival staining. 
The secondary hypotheses that will be tested will be that a one-month treatment of moderate to severe dry eye sufferers with an eyedrop / gel combination will reduce symptomatology upon waking.

Efficacy Endpoint(s)
	
The primary end points will be:
 
 i. OSDI total score; ii. Measured lissamine green bulbar conjunctival staining (mm²). 
The secondary end points will be symptomatology upon waking (VAS scale).

Efficacy Procedure(s)
	
The primary response procedures will be: i. OSDI questionnaire; ii. Digital photography of lissamine green staining of the exposed bulbar conjunctiva. The secondary response procedures will be: i. VAS comfort & symptomatology questionnaire;
 	

Safety Procedure(s)
	
The safety procedures will be biomicroscopy, identification of adverse events, measurement of Snellen Visual Acuity and identification of prevalence of adverse events.
	

Population Profiling Procedure(s)
	
The procedures to profile the population key characteristics will be: i. Demographics and ocular history questionnaire (including concomitant treatment); ii. OSDI questionnaire;
	

Experimental Design
	
 Retrospective  Prospective
	
 Non-Randomized  Randomized

	
 Single masked (participant)  Single masked (investigator)  Double masked  Sponsor masked  Open label
	
 Single group  Parallel group  Crossover  Contralateral

Run-in Product(s)	REFRESH® Contacts® Unitdose, a CE marked eye lubricant eyedrop, manufactured by Allergan Pharmaceuticals Ireland, containing 0.5% carboxymethylcellulose sodium.	
Test Product(s)	
The treatment regimen to be tested will be:
 
 i. Optive® Fusion™ a CE marked eyedrop, manufactured by Allergan Pharmaceuticals Ireland, containing 0.1% sodium hyaluronate, 0.5% carmellose sodium and 0.9% glycerol for daytime use. The eyedrop will be used as needed up to four times a day but at least twice a day. ii. Optive® Gel Drop a CE marked gel manufactured Allergan Pharmaceuticals Ireland, containing 0.5% carboxymethylcellulose sodium and 0.9% glycerol for night time use. The eyedrop will be used once in the evening; the gel drop being instilled any time during the last hour prior to sleep 	
Study Visits	
Three scheduled visits over a five-week period.
 
 i. Enrolment visit; ii. Baseline / Dispensing visit (7 ± 1 days from enrolment); ii. One month follow-up visit (30 ± 3 days from dispensing). 	
Keywords	Optive Fusion, Optive Gel Drops, Refresh Contacts Unitdose, OSDI, Conjunctival Staining, Tear Film Kinetics, Dry Eyes	
Regulatory Status	This trial requires Ethics Committee (EC) approval prior to initiation.	
Responsibilities	Sponsor	Name: Allergan Pharmaceuticals International Ltd. [REDACTED]
	CRO and Data Management	OCULAR TECHNOLOGY GROUP - International [REDACTED]
	Legal Representative (where applicable)	

2 Introduction and Rationale

2.1 Background

Tear film physiology differs greatly between the waking and sleeping periods. During the waking period the tear film is an aqueous based film produced by the lacrimal gland and connected to the ocular surface via the inner mucin layer, and protected from evaporation by the outer lipid layer. Aqueous, which accounts for 98% of the overall tear film, is distributed onto the ocular surface and a proportion of the aqueous is eliminated with each blink. In contrast, during sleep aqueous production stops and the tear film becomes a gel like structure dominated by mucin and lipids [1].

Anomalies of any of the layers of the tear film lead to dry eye complaints which vary greatly not only in their level of severity but also in their diurnal characteristics. Typically, dry eye complaints are least during the day and most marked either in the evening or upon waking, suggesting different potential mechanisms [2].

The physiological characteristics of the tear film would suggest that a different dry eye treatment should be implemented for the waking and sleeping phases of the day: aqueous supplementation and surface protection from the atmosphere during waking hours and gel supplementation during sleep; the latter being particularly important for those sufferers with highest level of complaints upon waking.

In addition to symptomatology, dry eyes are characterised by changes in the tear film and / or the ocular surface depending upon the patients. Reported tear film anomalies include destabilisation (shorter tear film break up time), poorer ocular surface coverage (decreased tear film kinetics) and increased tear film evaporation. The ocular surface modifications are corneal fluorescein staining and conjunctival (exposed bulbar and palpebral) lissamine green staining, the latter being the most prevalent. Another ocular tissue change reported is increased redness due to the inflammatory process associated with dry eye [3].

2.2 Objectives

The primary objectives of the study will be to:

- i. Quantify the effect of a one-month treatment involving an eyedrop / gel combination on overall dry eye symptomatology on moderate to severe dry eye sufferers;
- ii. Evaluate the effect of a one-month treatment involving an eyedrop / gel combination on conjunctival staining on moderate to severe dry eye sufferers.

The secondary objective of the study will be to:

Quantify the effect of a one-month treatment involving an eyedrop / gel combination on symptomatology upon waking on moderate to severe dry eye sufferers.

2.3 Hypothesis

The primary hypotheses that will be tested will be that:

- i. One-month treatment of moderate to severe dry eye sufferers with an eyedrop / gel combination will reduce overall dry eye symptomatology;
- ii. One-month treatment of moderate to severe dry eye sufferers with an eyedrop / gel combination will decrease conjunctival staining.

The secondary hypothesis that will be tested will be that:

One-month treatment of moderate to severe dry eye sufferers with an eyedrop / gel combination will reduce symptomatology upon waking.

2.4 Endpoints

The primary end points will be:

- i. OSDI total score.
- ii. Measured lissamine green bulbar conjunctival staining (mm²).

The secondary end points will be symptomatology upon waking (VAS scale).

3 Study Sponsor and Investigators

The Investigator will provide participants with a copy of the consent form written in a language the participant understands; in this study all documentation will be in English and only participants fluent in English will take part. The consent document will meet all applicable local laws and will provide participants with information regarding the purpose, procedures, requirements, and restrictions of the study, along with any known risks and potential benefits associated with participating, the available compensation, and the established provisions for maintaining confidentiality of personal, protected health information. Participants will be told about the voluntary nature of participation in the study and will be provided with contact information for the appropriate individuals should questions or concerns arise during the study. Participants also will be told that their records may be accessed by appropriate authorities and Sponsor-designated personnel. The Investigator must keep the original, signed copy of the consent and must provide a duplicate copy to each participant.

The study will be submitted to the IRAS centralized National Research Ethics Service (for proportionate review). The investigation will not start until approval has been received by the site.

4 Test Materials

4.1 Test Products

The treatment regimen will be:

- i. Optive® Fusion a CE marked eyedrop, manufactured by Allergan Pharmaceuticals Ireland, containing 0.1% sodium hyaluronate, 0.5% carmellose sodium and 0.9% glycerol for daytime use. The eyedrop will be used as needed up to four times a day but at least twice a day;
- ii. Optive® Gel Drop a CE marked gel manufactured by Allergan Pharmaceuticals Ireland, containing 0.5% carboxymethylcellulose sodium and 0.9% glycerol for night time use. The eyedrop will be used once in the evening; the gel drop being instilled any time during the last hour prior to sleep.

The treatment regimen will be used for one month (30 ± 3 days).

4.2 Run-in Product

The run-in product will be REFRESH® Contacts® Unitdose, a CE marked eye lubricant eyedrop, manufactured by Allergan Pharmaceuticals Ireland, containing 0.5% carboxymethylcellulose sodium. The eye drop will be used as needed up to four times a day but at least twice a day for one week (7 ± 1 days)

4.3 Adjunct Products

No other system will be used and the products will be used according to their indication and discarded at the completion of the period of use.

5 Test Population

5.1 Recruitment Procedure

The prospective participants will be selected from the existing clinical population of the OTG-i Research Clinic or recruited by means of an advertisement if necessary. The participants fulfilling the criteria for inclusion and none of the exclusion criteria will be invited in a random fashion to participate in the study until the test population is achieved.

The prospective participants will initially be contacted by telephone, the investigation will be explained in detail and if interested an enrolment / test visit will be scheduled. The prospective participants will be sent a copy of the Participant Information Sheet and Informed Consent by email prior to the visit, upon arrival at the clinic the participants will be given a printed copy of the consent form and the study will be explained to them. The participants will be asked to read and sign the Informed Consent prior to any evaluation.

5.2 Number of Participants

Up to 40 participants will be screened for 35 participants to be enrolled into the investigational phase at the end of Visit 2 with a view to achieve a cohort of 30 participants completing the study as per the protocol.

5.3 Inclusion and Exclusion Criteria

5.3.1 Inclusion Criteria

There are no requirements as to participant race, gender or occupation. In order to be enrolled, each participant shall meet the following criteria:

- i. At least 18 years old;
- ii. Moderate to severe dry eye symptomatology based up an OSDI score of ≥ 23 ;
- iii. Ocular comfort at waking <65 on 100-point scale;
- iv. Conjunctival staining Grade ≥ 2 (scale 0 to 4) in at least one eye;
- v. Use of eyedrops for the relief of dry eye symptoms for at least one month.
- vi. Have read and understood the Participant Information Sheet;
- vii. Have read, signed and dated the Informed Consent;
- viii. Best corrected visual acuity in each eye of at least 20/25
- ix. Have normal eyes with the exception of the need for visual correction; subjects must be willing to cease contact lens wear for the duration of the study;
- x. Be willing and able to adhere to the instructions set in the clinical protocol and maintain the appointment schedule.

5.3.2 Exclusion Criteria

To be eligible as a participant, each candidate shall be free of any ocular or medical condition that may affect the results of this study.

The following are specific criteria that exclude a candidate from enrolment in this study:

- i. Use of Benzalkonium Chloride (BAK) preserved eyedrops in the last month;
- ii. Use of Optive brand eyedrops in the last month;
- iii. [REDACTED]
- iv. Use of systemic or ocular medications for which test products could be contraindicated as determined by the investigator;
- v. Monocular participants (only one eye with functional vision).
- vi. Subjects unwilling or unable to cease contact lens wear for the duration of the study;
- vii. [REDACTED]
- viii. History of herpetic keratitis, ocular surgery or irregular cornea;
- ix. Known pregnancy or lactation during the study period;
- x. [REDACTED]
- xi. Participation in any clinical trial within 30 days of the enrolment visit;

5.4 Premature Withdrawal

A participant will be withdrawn from the investigation before completion if:

- i. The participant withdraws his/her consent to be included in the trial;
- ii. An adverse event takes place that is considered by the participant or the investigator to warrant withdrawal;

- iii. Any event that leads the investigator to believe that it is not in the best interest for the participant to continue in the study;
- iv. The study is prematurely terminated by the Principal Investigator, local research ethics committee or the Sponsor;
- v. The participant is lost to follow-up;
- vi. The participant no longer meets the eligibility criteria;
- vii. The participant dies.

5.5 *Informed Consent*

Each participant must give written consent according to local requirements after the nature of the study has been fully explained. The consent form must be signed before performance of any study-related activity. The consent form that is used must be approved by both the Sponsor and by the reviewing IEC. The informed consent must be in accordance with principles that originated in the Declaration of Helsinki, current ICH and GCP guidelines, applicable regulatory requirements, and sponsor policy.

Before entry into the study, the Investigator or an authorized delegated member of the investigational staff must explain to potential participants the aims, methods, reasonably anticipated benefits, and potential hazards of the study, and any discomfort it may entail. Participants will be informed that their participation is voluntary and that they may withdraw consent to participate at any time. They will be informed that choosing not to participate will not affect the care the participants will receive. Finally, they will be told that if needed their records may be accessed by health authorities and authorized sponsor staff without violating the confidentiality of the participant, to the extent permitted by the applicable law(s) or regulations.

The participants will be given sufficient time to read the informed consent form and the opportunity to ask questions. After this explanation and before entry into the study, consent must be appropriately recorded by means of the participant's dated signature. After having obtained the consent, a copy of the informed consent form must be given to the participants.

In the event that additional investigators / sites are added to the protocol, the informed consent will be modified to include the Investigator's name, address, phone number and 24-hour emergency number.

6 Study Design & Procedures

6.1 *General Description*

The study will be conducted as an open label, bilateral, prospective, interventional single arm clinical study, however, the investigator carrying out the tear film kinetics and tissue staining analyses post-hoc will be masked for these activities.

6.2 *Experimental Routine*

The participants will attend a total of three scheduled visits over a five-week period.

- i. Enrolment visit;
- ii. Baseline / Dispensing visit (7 ± 1 days from enrolment);
- ii. One month follow-up visit (30 ± 3 days from dispensing).

The participants will attend an initial Enrolment visit to obtain their informed consent, evaluate their suitability to take part in the investigation and collect their baseline information. The participants who fulfil the investigation inclusion and exclusion criteria will be dispensed with the run-in eyedrops to be used for one

week. Subjects who wear contact lenses will be required to cease wear during this run-in period (and continue to do so for the duration of the study). At the completion of the one-week run-in period the participants will attend the clinic for baseline measurements and dispensing of the study products. The participants will use the study products as per the study protocol for the remainder of the study. The Baseline and One-month visits will be scheduled in the morning. The participants will not take part in any concomitant investigation of any type or take concomitant medications not allowed by the exclusion criteria.

The participants will complete weekly time stamped questionnaires sent in electronic format using [REDACTED] secure electronic survey software using either a personal computer, Apple Mac, tablet or smart phone to characterise the time scale of the improvement that may be achieved.

Two visual analogue scale questionnaires will be sent on each occasion: one overnight to capture symptomatology upon waking and one late afternoon to be completed prior to sleep to capture daytime and evening symptomatology. In addition, the participants will complete the OSDI questionnaire one and four weeks after test product dispensing.

6.3 Measures to Avoid Bias

6.3.1 Randomization

There is no randomization in this study.

6.3.2 Masking

All videos and images will be anonymized and randomized by an unmasked technician prior to analysis. The investigators conducting the post hoc analyses of the Tearscope videos and digital images will be masked with respect to the participant ID and visit.

6.4 Test Procedures

6.4.1 Efficacy Procedures

The primary response procedures will be:

- i. OSDI questionnaire;
- ii. Digital photography of lissamine green staining of the exposed bulbar conjunctiva.

The secondary response procedure will be:

- i. VAS comfort & symptomatology questionnaire ;

[REDACTED]

6.4.2 Safety Procedures

The procedures to monitor safety will be:

- i. Identification and prevalence of adverse events;
- ii. Measurement of Snellen visual acuity;

iii. Safety ocular integrity (biomicroscopy).

6.4.3 Population Profiling Procedures

The procedures to profile the population key characteristics will be:

- i. Demographics and ocular history questionnaire (including concomitant treatment).
- ii. OSDI questionnaire.

[REDACTED]

[REDACTED]

[REDACTED]

[REDACTED]

[REDACTED]

[REDACTED] aire

xiii. Scheduling

¹ The participants will be given full details of the investigation at the time of making the appointment for the enrolment visit. The explanation at the time of the visit will be to reinforce the information given during the initial telephone contact and answer any questions the participants may have.

[REDACTED]

[REDACTED]

7 Statistical Analysis and Sample Size Determination

7.1 Determination of Sample Size

A sample size of 27 achieves 81% power to detect superiority using a one-sided t-test when the OSDI margin of equivalence is 7.5 and the true difference between the baseline and the follow-up value is 10.0, the data being drawn from a single population with a within participant standard deviation of 5.0 and with the significance level (alpha) of the test being set at 0.050. Based upon the intended cohort sample it is proposed to screen 40 participants to have 35 participants enrolled into the investigational phase at the end of Visit 2 to achieve a cohort of 30 participants completing the study as per the protocol.

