3.5.1 General

The study design does not include a control group the efficacy of the regimen will be measured by comparing the data recorded at the dispensing visit, prior product dispensing visit (Baseline) to the data recorded at the 30-Day follow-up visit (Response).

In this study two sets of analyses will be carried out for each primary and secondary variables. The first set will follow a linear model approach to account for all the data characteristics (e. g. multiple data for the same response variable for a given timepoint). The second set will be based on simplistic testing such as the t-test or if not applicable an equivalent non-parametric test.

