3.5.2 Primary Endpoints

LINEAR MODEL ANALYSIS

The primary variables OSDI total score and measured lissamine green bulbar conjunctival staining are parametric variables.

The primary variables being continuous variables ideally parametric testing will be carried out. Therefore, if the variables are normality distributed or close to normally distributed before or after transformation allowing parametric analysis parametric statistics will be carried out using the following model:

OSDI Total Score: A linear mixed model will be used. The model will include time (Baseline / Dispensing visit, One-month follow-up visit) as repeated measures fixed factor. The subject ID will be a random factor. The covariance structure that best models the residuals errors from the same subject across the time periods will be selected according to the AICC criterion. Possible structures will include Compound Symmetry (CS), Heterogeneous Compound Symmetry (CSH), Ante-Dependent (ANTE (1)), Autoregressive (AR1), Unstructured (UN). In case that the Hessian Matrix is not positive definite, random effect will be removed from the model. The comparisons of OSDI scores between baseline and one month follow up will be carried out using a 95% confidence interval from the least square mean differences in percentage from the mixed linear model.

Lissamine green bulbar conjunctival staining: A linear mixed model will be used. The model will include time (Baseline / Dispensing visit, One-month follow-up visit), region (nasal and temporal) as repeated measures fixed factors as well as with all the possible interactions. The eye will be taken into consideration as repeated measure but not as fixed factor. The subject ID will be a random factor. The covariance structure that best models the residuals errors from the same subject across the time and eye will be selected according to the AICC criterion. Possible structures will include Compound Symmetry (CS), Heterogeneous Compound Symmetry (CSH), Ante-Dependent (ANTE (1)), Autoregressive (AR1), Unstructured (UN). In case that the Hessian Matrix is not positive definite, random effect will be removed from the model. The comparisons of Lissamine green bulbar conjunctival staining between baseline and one month follow up will be carried out using a 95% confidence interval from the least square mean differences in percentage from the mixed linear model.

If the variables cannot be normalized the following model will be applied:

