OSDI Total Score: A generalized mixed linear model will be used. Possible models will include Gamma regression model with a Log link function or a Negative Gaussian with Log link function. The model will include time (Baseline / Dispensing visit, One-month follow-up visit) as repeated measures fixed factors. The subject ID will be a random factor. The covariance structure that best models the residuals errors from the same subject across the time and eye will be selected according to the AICC criterion. Possible structures will include Compound Symmetry (CS), Heterogeneous Compound Symmetry (CSH), Ante-Dependent (ANTE (1)), Autoregressive (AR1), Unstructured (UN). In case that the Hessian Matrix is not positive definite, random effect will be removed from the model. The comparisons of OSDI score between baseline and one month follow up will be carried out using a 95% confidence interval from the least square mean differences in percentage from the generalized mixed linear model.

Lissamine green bulbar conjunctival staining: A generalized mixed linear model will be used. Possible models will include Gamma regression model with a Log link function or a Negative Gaussian with Log link function. . A linear mixed model will be used. The model will include time (Baseline / Dispensing visit, One-month follow-up visit), region (nasal and temporal) as repeated measures fixed factors as well as with all the possible interactions. The eye will be taken into consideration as repeated measure but not as fixed factor. The subject ID will be a random factor. The covariance structure that best models the residuals errors from the same subject across the time and eye will be selected according to the AICC criterion. Possible structures will include Compound Symmetry (CS), Heterogeneous Compound Symmetry (CSH), Ante-Dependent (ANTE (1)), Autoregressive (AR1), Unstructured (UN). In case that the Hessian Matrix is not positive definite, random effect will be removed from the model. The comparisons of Lissamine green bulbar conjunctival staining between baseline and one month follow up will be carried out using a 95% confidence interval from the least square mean differences in percentage from the generalized mixed linear model.

SIMPLISTIC SINGLE FACTOR ANALYSIS

The primary variables OSDI total score and measured lissamine green bulbar conjunctival staining are parametric variables.

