The primary variables being continuous variables ideally parametric testing will be carried out. Therefore, if the variables are normality distributed or close to normally distributed before or after transformation allowing parametric analysis parametric statistics the following test will be applied:

OSDI Total Score: A paired t-test approach will be followed. The test will compare the OSDI scores recorded at the two visits (Baseline / Dispensing visit, One-month follow-up visit). The comparisons of the OSDI scores between baseline and one month follow up will be carried out taking 95% as the threshold of significance.

Lissamine green bulbar conjunctival staining: A paired t-test approach will be followed. Lissamine green bulbar conjunctiva staining is recorded and quantified separately for the right and left eyes and for the nasal and temporal bulbar regions; therefore, in order to prevent sample size overestimation by accounting for each measurement the analysis will be carried out on the mean staining of the two zones of the two eyes to have a single data point per visit. The test will compare the mean staining recorded at the two visits (Baseline / Dispensing visit, One-month follow-up visit). The comparisons of the mean staining between baseline and one month follow up will be carried out taking 95% as the threshold of significance.

If the variables cannot be normalized the following test will be applied:

OSDI Total Score: the non-parametric equivalent of the paired t-test is Wilcoxon Rank Test. The test will compare the OSDI scores recorded at the two visits (Baseline / Dispensing visit, One-month follow-up visit). The comparisons of the OSDI scores between baseline and one month follow up will be carried out taking 95% as the threshold of significance.

Lissamine green bulbar conjunctival staining: the non-parametric equivalent of the paired t-test, is Wilcoxon Rank Test. The test will compare the mean staining of the two measurement zones of the two eyes to produce a single data point per visit (Baseline / Dispensing visit, One-month follow-up visit). The comparisons of the mean lissamine green staining between baseline and one month follow up will be carried out taking 95% as the threshold of significance.

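### The 81% power in Protocol 7.1 belongs to a test that the OSDI reduction exceeds 7.5 points; no planned OSDI test carries that margin

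*Protocol*

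**What the plan says.** Protocol 7.1 (Determination of Sample Size) bases the sample size on OSDI alone. It describes detecting "superiority using a one-sided t-test when the OSDI margin of equivalence is 7.5 and the true difference" between baseline and follow-up is 10.0. The other inputs are an SD of 5.0, described as within participant, alpha 0.050, 27 participants and 81% power. The plan is to enrol 35 so that 30 complete.

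The rest of the visible text has no 7.5-point margin:

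- Protocol 2.3 states only that the "gel combination will reduce overall dry eye symptomatology".
- SAP 2.2 compares the follow-up OSDI mean directly with the baseline mean, in one-sided form. The direction is reversed: the alternative is written as a higher follow-up score, although the sentence above it predicts a reduction.
- SAP 3.5.1 says "two sets of analyses will be carried out for each primary and secondary variables". It does not say which set decides.
- SAP 3.5.2, linear model: OSDI is compared "using a 95% confidence interval from the least square mean differences in percentage from the mixed linear model". If OSDI cannot be normalised, a generalised model replaces it: "Possible models will include Gamma regression model with a Log link function".
- SAP 3.5.2, simple analysis: "A paired t-test approach will be followed. The test will compare the OSDI scores recorded at the two visits". The comparison "will be carried out taking 95% as the threshold of significance", with no mention of one or two sides. A Wilcoxon test is the fallback.
- SAP 3.3 allows square-root, log or inverse transformation if normality fails.

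**The concern.** A power statement should describe the test that will be run. Here it describes a demanding test (a fall of more than 7.5 points), while the SAP runs an easier one (any fall). A report that sets the Protocol 7.1 sentence beside a significant SAP result would invite the reader to think that a reduction beyond 7.5 points had been tested. This is a primary endpoint of an open-label, single-arm study, so whether the fall is merely non-zero or exceeds a set margin matters to its reading.

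**Working it through.** **Inputs** (all from Protocol 7.1): n = 27, true fall 10.0, margin 7.5, SD 5.0, one-sided alpha 0.05, 30 planned completers.

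**1. Reproduce the plan's figure.** Take 5.0 as the SD of the paired change. The noncentrality is (true fall − margin)/SD × √n = (10.0 − 7.5)/5.0 × √27 = 0.5 × 5.196 = 2.598, on 26 degrees of freedom. Power from the non-central t is **81.2%**, which matches. At n = 26 it is 79.8%, and at n = 30 it is 84.8%. The margin is what yields 81% at 27.

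**2. Power of the planned test (no margin), same inputs.** The noncentrality is 10.0/5.0 × √27 = 10.39. Power exceeds **99.9%** at n = 27 and n = 30. For a test against zero, 81% power at n = 27 (one-sided 0.05) belongs to a true fall of 2.5 points, not 10.

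**3. Mean fall needed at n = 30, SD 5.0.** The standard error is 5/√30 = 0.913; t is 1.699 (one-sided 0.05) or 2.045 (two-sided 95%).

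| Test | One-sided 0.05 | Two-sided 95% |
|---|---|---|
| Against zero (planned) | 1.699 × 0.913 = 1.55 | 2.045 × 0.913 = 1.87 |
| Against 7.5 (powered) | 7.5 + 1.55 = 9.05 | 7.5 + 1.87 = 9.37 |

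A mean fall between the two rows meets the planned test and fails the powered one. If the true fall is exactly 7.5, the margin test succeeds 5% of the time and the zero-difference test more than 99.9%.

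**4. Sidedness.** If the margin is judged by a two-sided 95% interval, the form used in the SAP models, margin-test power is 71% at n = 27 and 75% at n = 30.

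**5. Percentage output.** A percentage interval has no fixed equivalent of 7.5 points. For assumed baseline means of 23 (the entry cut-off), 40 and 60, 7.5 points is 7.5/23 = 33%, 7.5/40 = 19% and 7.5/60 = 12.5%.

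**6. Meaning of the SD.** If 5.0 is instead a per-visit SD and the visits are independent, the SD of the change is 5 × √2 = 7.07. Margin-test power (one-sided 0.05) is then 56% at n = 27 and 60% at n = 30. The zero-difference test for a true fall of 10 still exceeds 99.9%.

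**7. A power statement that would fit the zero-difference test.** At n = 30 and an SD of change of 5.0, 80% power is reached at a true fall of 2.325 points (one-sided 0.05) or 2.646 (two-sided). Rounded up, 2.4 gives 82.2% and 2.7 gives 81.6%. With an SD of 7.07 these become 57% and 52%.

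**The case against.** The strongest reply is that the mismatch is conservative: the sample was sized for a harder test than the one planned, and no visible text promises a claim beyond 7.5 points. That stands. A reader might infer from the mismatch that the study is too small, or that the sponsor intends such a claim. The documents support neither. The reply does not remove the fault, because the 81% still belongs to a test that is not planned.

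A reader might also infer that a 7.5-point comparison could never be obtained from the planned output. That goes too far. If the paired t-test is run on untransformed scores, the mean change and its standard error give an interval in points. But no such interval or comparison is specified, and transformation, the Wilcoxon fallback or the percentage models would not provide one.

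Nor is sidedness simply absent: Protocol 7.1 and the form of the SAP 2.2 hypotheses are one-sided. The gap is that SAP 3.5.2 uses 95% intervals and an unspecified 95% threshold without linking them to those hypotheses.

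Finally, reproducing 81% shows how 5.0 was used, not what it measures. The documents give no source for it, so its meaning is a question for the sponsor.

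Some text is redacted, but the OSDI hypotheses and tests can be read in full, so redaction does not account for the missing margin there.

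**Conclusion.** The point holds as a mismatch between the power statement and the planned OSDI tests; it should be fixed, and it is not a sample-size failure. The stated 81% is arithmetically right for a one-sided 0.05 test against a 7.5-point margin, if 5.0 is the SD of the paired change. The planned tests carry no margin, and a significant result from them would show only a reduction beyond zero. The thresholds of 1.55 or 1.87 against 9.05 or 9.37 points rest on an observed SD of change of 5.0 and 30 completers, with OSDI analysed untransformed. The reversed OSDI hypotheses in SAP 2.2 are a separate error and do not add to the weight of this point.

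**What to change.** Before results are seen, adopt one option.

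**A. Carry the margin into the analysis.** In SAP 2.2 and 3.5.2, specify a paired t-test on untransformed OSDI points as the deciding OSDI test: H0 mean reduction (baseline minus follow-up) ≤ 7.5, H1 > 7.5, one-sided 0.05. Exempt it from SAP 3.3 transformation and make the other models supportive. If a two-sided 95% interval is used instead, restate power as 71% (n = 27) or 75% (n = 30).

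**B. Keep the zero-difference test.** Remove the margin and the 81% from Protocol 7.1 and claim no reduction beyond 7.5 points. State that, with 30 completers and an SD of the paired change of 5.0, the paired t-test on untransformed OSDI has at least 80% power for a true fall of 2.4 points (one-sided 0.05) or 2.7 points (two-sided 95%). Exempt that test from SAP 3.3 transformation, or say that the power figure applies only to untransformed data. Report the mean change in OSDI points with its confidence interval.

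**Under either option:**

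- Have the sponsor confirm that 5.0 is the SD of the paired change. If it is not, restate the power; the 7.07 results above show how far it could move.
- State one sidedness consistently in Protocol 7.1, SAP 2.2 and SAP 3.5.2.
- Separately, reverse the OSDI hypotheses in SAP 2.2 so that the alternative is a reduction.

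**Cost:** wording changes to the protocol and SAP, with the principal investigator, sponsor and ethics committee approvals that Protocol 13.3 requires for plan modifications. Enrolment and visits do not change. Option A sets a harder success criterion; option B gives up any claim beyond 7.5 points.
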